### 8.3. Variables

Table I. Diagnoses of diseases

Variable (Disease)	Role	Data Source	Operational Definition (AD ICD-10 diagnostic code)
Atopic dermatitis	Demographic characteristics, inclusion criteria	National Patient registry	L20.x
Inflammatory Bowel Disease	Demographic characteristics, exclusion criteria	National Patient registry	K50, K51
Psoriatic Arthritis	Demographic characteristics, exclusion criteria	National Patient registry	M07.0, M07.1, M07.2, M07.3
Psoriasis	Demographic characteristics, exclusion criteria	National Patient registry	L40
Rheumatoid arthritis 	Demographic characteristics, exclusion criteria	National Patient registry	M05.x and M06.x (except M06.1)

Table II. International Anatomical Therapeutical Chemical (ATC) codes and treatment procedure (SKS) codes.

#### Systemic treatment for AD (conventional disease-modifying antirheumatic drugs (DMARDs))

090177e1a4d83c92\Approved\Approved On: 11-Nov-2025 17:27 (GMT)

Variable (Exposure)	Role	Data Source	Operational Definition (ATC Code)	Operational Definition (SKS Code)
Cyclosporine	Treatment	Registry of Medicinal Products Statistics	L04AD01	BOHJ20
Methotrexate	Treatment	Registry of Medicinal Products Statistics	L01BA01 / L04AX03	BWHA115
Azathioprine	Treatment	Registry of Medicinal Products Statistics	L04AX01	BWHB83
Mycophenolic Acid	Treatment	Registry of Medicinal Products Statistics	L04AA06	BOHJ22B
Prednisolone	Treatment	Registry of Medicinal Products Statistics	H02AB*	MH02AB*

**Systemic treatment for AD and other indications (biological therapy and targeted synthetic DMARDs)**

Variable (Exclusion criteria)	Role	Data Source	Operational Definition (ATC Code)	Operational Definition (SKS Code)
Baricitinib	Treatment, exclusion criteria	Registry of Medicinal Products Statistics	L04AF02	BWHP106
Upadacitinib	Treatment, exclusion criteria	Registry of Medicinal Products Statistics	L04AF03	BWHP107
Dupilumab	Treatment, exclusion criteria	Registry of Medicinal Products Statistics	D11AH05	BOHJ18B8

Table III. Outcomes.

Variable (ICD-10 diagnostic code description)	Role	Data Source	Operational Definition (ICD-8 diagnostic code)	Operational Definition (ICD-10 diagnostic code)
Dyslipidemia	AE, sec. outcome	National Patient registry		E78 (pre-defined macro)
Herpes zoster 			053.00–053.9	B02
		MACE 		
Stroke	AE, part of primary outcome (MACE)	National Patient registry	NA	I61, I63, I64
Myocardial Infarction	AE, part of primary	National Patient registry	NA	I21, I22

090177e1a4d83c92Approved\Approved On: 11-Nov-2025 17:27 (GMT)

	outcome (MACE)			
CV death (cause of death) 	AE, part of primary outcome (MACE)	National Patient registry	NA	Cause of Death: ICD10: I20-25, I60-61, I63-64, I69, G45.8-45.9, I71, I74, I11.0, I13.0, I13.2, I50, Z95, I46.1, I65, I66, I67.0, I67.2, I70.
Malignancies				
Malignancies, excluding NMSC	AE, co-primary outcome (Malignancy)	National Patient registry	140-209 (except 173)	C00-C99, expect C44
NMSC	Exclusion criteria	National Patient registry	173	C44
Serious infections 	AE, sec. outcome	National Patient registry	Table V	Table V
Arterial thromboembolisms (AT) Venous thromboembolism Deep vein thrombosis (DVT) and pulmonary embolism (PE) 	AE, sec. outcomes	National Patient registry	DVT: 451 PE: 450.99 AT: 444	DVT: I801, I80.2, I80.3, I80.8, I80.9, I82.2, I82.3, I82.9 PE: I26 AT: I74 And anticoagulation therapy: ATC B01A

Table IV. ICD-8 and ICD-10 for medical history

Variable (ICD-10 diagnostic code description)	Role	Data Source	Operational Definition (ICD-8 diagnostic code)	Operational Definition (ICD-10 diagnostic code)	Operational Definition (Nordic Medico-Statistical Committee (NOMESCO) Classification of Surgical Procedures codes)
Alcohol abuse	medical history	National Patient registry	291, 303	F10.1–10.9 (pre-defined macro)	NA
Heart failure	medical history	National Patient registry	NA	I11.0, I13.0, I42, I50	NA
CVD Risk Factors					

090177e1a4d83c92ApprovedApproved On: 11-Nov-2025 17:27 (GMT)

History of coronary heart disease 	medical history	National Patient registry	NA	I20-I25	PCI (KFNG00, KFNG02, KFNG02A, KFNG05, KFNG05A, KFNG10, KFNG12, KFNG20, KFNG22, KFNG30, KFNG40, KFNG96, KZFX01) or CABG (KFNA, KFNB, KFNC, KFND, KFNE, KFNF, KFNH, KFNJ, KFNK, KFNW)
Diabetes	medical history	National Patient registry	250	E10-E14 (pre-defined macro)	NA
Dyslipidemia (within the past 5 years)	medical history	National Patient registry	NA	E78 (pre-defined macro)	NA
History of cancer	medical history	National Patient registry	140-209	C00-C96	NA
Hypertension	medical history	National Patient registry	400-404 (pre-defined macro)	I10.x-I15.x (pre-defined macro)	NA
Smoking history	medical history	National Patient registry	NA	Pre-defined macro	NA

Table V. ICD-10 Serious infection (see table III, role for all: AE and Secondary Outcome; Data Source: National Patient Registry)

Serious infections	Operational Definition: ICD-10
CNS infections	A02.21, A06.6, A17.0, A20.3, A27.81, A32.1, A39.0, A80-A89, B00.3, B00.4, B01.0, B01.1, B02.0-B02.2, B05.0, B05.1, B06.0, B26.1, B26.2, B10.01, B37.5, B38.4, B43.1, B45.1, B46.1, B58.29, G00-G08

090177e1a4d83c92\Approved\Approved On: 11-Nov-2025 17:27 (GMT)

Gastrointestinal infections	A00, A01, A02.0, A02.8, A02.9, A03-A05, A06.0, A06.2-A06.4, A07-A09, A21.3, A22.2, A42.1, B05.4, B15-B19, B25.1, B46.2, K35, K37, K57, K61, K62.0, K65.0, K65.9, K67, K75.0, K81.0, K81.8, K81.9
Gynecological infections	N70.0, N70.9, N71.0, N71.9, N72, N73.0, N73.2, N73.3, N75.5, N73.8, N73.9, N74
Heart infections	A32.8, B33.21, B37.6, I00, I01, I30, I32, I33, I38-I41, I43.0
Hepatitis	B16, B17, B18
HIV	B20-B24
Musculoskeletal infections	A02.23, H05.029, M00-M03, M46.2, M46.3, M46.5, M46.6, M60.0, M65.0, M65.1, M71.0, M71.1, M86.0-M86.2, M86.8, M86.9, M90.0, M90.1, M90.2
Opportunistic infections	A02, A07.2, A07.3, A15-A19, A27.0, A31, A32, A40.3, A42-A44, A48.1, A48.1, A60.0, A81.2, B00-B02, B17.9, B25, B27.1, B37-B40, B44, B45, B55, B58, B59, B78, B95.3, G02.0, G02.1, J13, J17.1, J17.2, K23.0, K67.3, K93.0
Pulmonary infections	A48.1, A37, B39-B40, B01.2, B05.2, B25.0, B44, B58.3, B59, B95.3, J10-J22, J85, J86, U04
Sepsis	A02.1, A20.7, A22.7, A24.1, A26.7, A28.2B, A32.7, A40, A41, A42.7, B37.7, R65.0, R65.1, R65.9
Skin and subcutaneous tissue infections	A36.3, A60, B00.1, B00.2, B00.7, B00.9, B01.8, B01.9, B02.3-B02.9, B05.3-B05.9, B08, B09, B35, B36, L00-L05, L08, K11.3, K11.4, K11.6, K12.2, K06.8, K06.9, L30.3, M72.6
Tuberculosis	A19, K23.0, K67.3, K93.0, M01.1, M49.0, M90.0, N33.0, N74.1, N74.1
URTI	A18.6, A36.8, A36.9, H39.0, H39.1, H60.0-H60.3, H60.9, H61.0, H65.0, H65.1, H65.9, H66.0, H66.4, H66.9, H67.1, H70.0, H70.2, H70.8, H70.9, J01, J02, J06, J36
UTI	A54.0-A54.2, N80, N10, N12, N13.6, N15.1, N15.9, N16.0, N30.0, 30.3, N30.9, N34.0, N34.1, N34.2, N39.0, N41.0, N41.2, N45

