### **Registries utilized in this study:**

The Danish National Patient Registry (DNPR) holds information on inpatient visits (since 1977) and outpatient visits (since 1995), along with data on medical procedures, including hospital-administered biologics and phototherapy. Diagnoses are recorded based on the International Classification of Diseases (ICD-8 from 1977 to 1993 and ICD-10 from 1994 onward). Hospital-administered procedures and treatments are registered using the SKS codes, while surgical procedures have been recorded according to the NOMECCO Classification of Surgical Procedures (NCSP) since 1996.

The Danish Register of Medicinal Product Statistics contains information on all filled prescriptions at community pharmacies from 1995 onwards, using the Anatomical Therapeutic Chemical (ATC) classification system.

The National Cause of Death Registry holds information on the cause and date of death when applicable.

The National Population Registry contains demographic information, including vital status and gender.

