## Events

During the treatment series, an adverse event can be adjudicated to the ongoing treatment. In the intention-to-treatment (ITT) study design, the event can be adjudicated to the treatment initiated at the index date.

If a patient is receiving overlapping treatments, any adverse event occurring during both therapies will be adjudicated to the therapy the patient has been on for the longest duration. Such events are referred to as overlapping events.

In the primary analyses, for overlapping events, the event is assigned to the drug the patient has been on the longest.

Multiple sensitivity analyses will be conducted to address overlapping events:

- The event is assigned to the most recent drug.
- The event is attributed to both drugs.
- The event is attributed to neither drug and the patient is censored.

Serious infections are defined as those requiring hospital admission for more than one day (Table V), and infections with HIV, hepatitis B or C, tuberculosis, or infections resulting in death.

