Incidence rates of additional adverse events of special interest (All-cause mortality, Arterial thromboembolisms, Venous thromboembolisms, Dyslipidemia, Herpes zoster, NMSC, Serious infections) will be presented per 10,000 person-years at risk with 95% confidence intervals. The incidence rates will be reported for each group separately (Groups a) a dermatologist-verified adult patient population with atopic dermatitis (AD) receiving conventional systemic treatments as per inclusion/exclusion criteria, b) cohort-matched

general Danish population and c) cohort-matched patients with AD not receiving systemic treatment (see section above for matching criteria)).

For group a, the incident rates will be presented per individual conventional systemic treatment (see table II).

In cases where patients received two systemic treatments or more during the data collection period, each treatment series will be analyzed independently. The statistical analysis will be captured in a statistical report with aggregated data in tables.

In the primary analyses, overlapping events will be attributed to the drug to which the patient has been exposed for the longest duration.

Tertiary statistical analysis:

Comparison of the identified adverse events per individual conventional treatment (table II) with the following two matched groups: a cohort-matched general Danish population and a cohort-matched patients with AD not receiving systemic treatment (see section above for matching criteria).

The groups will be compared using a Cox-regression models. The proportionality assumptions will be tested using Schoefeld test and plots. If the PH assumption is violated, we will allow time-varying effects by including covariate $\times$ log(time) interactions or using time-split intervals. Use of competing-risk models will be employed where relevant and feasible. The statistical analysis will be captured in a statistical report with aggregated data in tables. In the primary analyses, overlapping events will be attributed to the drug to which the patient has been exposed for the longest duration.

P-values may be reported when relevant for descriptive purposes and will not be adjusted for multiple testing; they are presented as descriptive statistics only, and no hypotheses are being tested.

A sensitivity analysis will be conducted requiring only one use of a drug to fulfil the inclusion criteria.

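### Table III counts VTE and arterial thromboembolism only with an ATC B01A record and gives no route for fatal or hospital-only treated events, so some true events, most clearly fatal PE, are missed.

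*Protocol*

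**What the plan says.** Protocol Section 8.3, Table III, puts AT, DVT and PE in one row. After the three ICD-10 code lists it adds "And anticoagulation therapy: ATC B01A". The row gives no time window, no SKS code and no exception for death, and it names only the National Patient Registry as data source.

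Section 8.4 describes the registers used:
- The Register of Medicinal Product Statistics "contains information on all filled prescriptions at community pharmacies from 1995 onwards, using the Anatomical Therapeutic Chemical (ATC) classification system".
- For the patient registry, "Hospital-administered procedures and treatments are registered using the SKS codes".
- "The National Cause of Death Registry holds information on the cause and date of death when applicable".

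Two other outcomes treat deaths differently. The cardiovascular-death component of MACE in Table III is defined by a list that begins "Cause of Death: ICD10: I20-25, I60-61, I63-64, I69, G45.8-45.9, I71, I74". In Section 8.7 (Events), serious infections include "infections resulting in death".

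VTE and AT are secondary outcomes. Under Section 8.7 their incidence rates "will be presented per 10,000 person-years at risk with 95% confidence intervals", and the same events enter the tertiary Cox comparisons with the two matched cohorts.

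**The concern.** The drug condition is joined to the diagnosis code by an and. With the sources listed, it can be met only through a community-pharmacy fill. Someone who dies before any fill, or whose anticoagulation was given only in hospital, has the event but may not have the record. The rule can therefore remove some of the most severe events from two safety outcomes.

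At stake are the absolute VTE and AT rates per drug, which the study sets out to supply, and possibly the comparisons built on them. Section 8.9 takes the view that outcomes this severe are unlikely to be misreported, but here the under-ascertainment would come from the definition itself. None of the sensitivity analyses listed in Section 8.7 varies an outcome definition, so the report would not reveal the effect.

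**Working it through.** The protocol gives no VTE or AT rate, no validity figure for the code-plus-drug definition and no sample-size calculation, so there is no figure to reproduce. The check has two parts.

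**1. Which events can be counted, reading the sections together**

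| Event | VTE or AT outcome (Table III) | Counted elsewhere |
|---|---|---|
| Survivor with a B01A fill | Counted | – |
| Survivor treated only in hospital, no B01A record | Not counted; no SKS code in the row | No |
| Fatal AT (I74), no B01A record | Not counted | Cardiovascular death within MACE; all-cause mortality |
| Fatal PE (I26), no B01A record | Not counted | All-cause mortality only |

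The last line rests on the full cardiovascular-death list in Table III, which contains I74 but not I26, I80 or I82. By contrast, Table II gives each study drug both an ATC and an SKS code, and serious infections have an explicit fatal route.

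**2. Illustration of size (all inputs are assumptions)**

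Let f be the share of true events with no B01A record, PPV the predictive value of the code alone, and g the share of false codes that still meet the drug condition. Then

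reported rate / true rate = (1 − f) + g × (1/PPV − 1).

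*No false codes counted (g = 0).* For an assumed true rate of 20 per 10,000 person-years:
- f = 5%: 20 × 0.95 = 19.0
- f = 10%: 20 × 0.90 = 18.0
- f = 20%: 20 × 0.80 = 16.0
- f = 30%: 20 × 0.70 = 14.0

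*Some false codes counted (PPV = 0.8, f = 20%, so 1/PPV − 1 = 0.25).*
- g = 0: 0.80
- g = 0.25: 0.80 + 0.0625 = 0.86
- g = 0.5: 0.80 + 0.125 = 0.925
- g = 1: 0.80 + 0.25 = 1.05

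With these inputs the net effect stays downward unless g exceeds 0.20/0.25 = 0.8, that is, unless more than 80% of false codes also carry a B01A record.

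*Code alone, without the drug condition.* Reported/true = 1/PPV, which is 1.11, 1.25 and 1.43 for PPV of 0.9, 0.8 and 0.7. Dropping B01A altogether would therefore replace one error with another.

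*Rate ratio.* With g = 0, the distortion factor is (1 − f in treated) / (1 − f in comparator):
- 10% and 10%: 1.00
- 20% and 10%: 0.80/0.90 = 0.89
- 10% and 20%: 0.90/0.80 = 1.13
- 30% and 10%: 0.70/0.90 = 0.78

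The direction depends entirely on which group loses more, and the protocol gives no information on that.

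**The case against.** Pairing a code with treatment is a recognisable way to gain specificity: it removes false codes as well as some true events. The row cites two sources for its definition that cannot be consulted here. This stands, and it is why the understatement is called probable and why the drug criterion should be kept for survivors.

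A reader might infer that fatal and hospital-only events can never qualify. The text does not go that far. Table III sets no window or sequence, so an earlier B01A record, even an unrelated one, would satisfy it as written. Only events with no B01A record are lost.

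A reader might also infer that the hazard ratios are biased in a known direction. Nothing in the protocol supports that. Equal loss leaves the ratio at 1.00, and unequal loss can move it either way.

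The data-source column is weak evidence. It is loose elsewhere too: the cardiovascular-death row names only the patient registry, although a separate Cause of Death Registry is described. Section 8.4 mentions a Hospital Medicines Registry in passing, but does not list it among the registers used. The flattened table leaves a small doubt whether the drug condition governs all three code lists or only the last, AT; its position after all of them favours all three.

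Finally, severe events do not vanish from the study. Every death counts in all-cause mortality, and fatal AT reaches MACE. That limits the damage but does not repair the VTE and AT rates. Windows and event dating could be left to the SAP, but the outcome rule is stated in the protocol, and as stated it has no fatal route.

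**Conclusion.** The point holds in a limited form. As written, the definition misses fatal and hospital-only treated VTE and AT that have no B01A record. Fatal PE is the clearest case, because no other cause-specific outcome picks it up. The secondary VTE and AT rates are probably too low by an amount that the protocol does not allow anyone to compute. An assumed loss of 5% to 30% gives rates 5% to 30% too low if no false codes are counted, and less, or even a slight excess, if many are. Hazard ratios are affected only if the loss differs between treated and comparator patients. The primary endpoint is not affected by this rule.

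The conclusion assumes that B01A is read from the community-pharmacy register, the only ATC-coded source listed, and that the condition applies to all three code lists. The change should be made, since the outcomes are safety outcomes and the remedy is cheap. It is not a reason to doubt the primary results.

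**What to change.** In Table III, replace the single drug condition for DVT, PE and AT with a rule that counts an event, dated at diagnosis, when any of these applies:
- the ICD code is followed by a B01A record within a stated window;
- the ICD code is followed by death within a fixed short window;
- PE, DVT or AT is the registered cause of death, dated at death if there is no earlier diagnosis.

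Name the Register of Medicinal Product Statistics and the Cause of Death Registry as sources in that row, beside the patient registry. Make explicit that the rule covers all three conditions. Add the code-only definition as a sensitivity analysis. This also covers survivors treated only in hospital, whom the revised main definition still leaves out.

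The cost is one table row and one further set of results from registers the study already uses. The downside is slightly lower specificity for the added fatal events. The code-only rates should be read as likely to include false codes.

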### **Validation of registries and endpoints:**

The Danish registries are widely used in epidemiological research and known for their high-quality longitudinal data and validity of these. Input of data into the registries and the following use of this is managed by the Danish Health Data Authorities (Sundhedsdatastyrelsen); a public authority that follows national guidelines, laws and regulations. Specifically, the Danish Health Data Authorities manages all national health registries such as the CPR-registry, National Patient Registry, Hospital Medicines Registry etc.. Use of these data for research is handled via Statistics Denmark, as describes below.

A recent study successfully validated the ICD-10 AD diagnosis code in the DNPR^14. No formal validation studies of all study endpoints have been performed. However, the validity of cardiovascular diagnoses in the DNPR has been investigated and overall found to be high and sufficient for use in research since 2010^15. In addition, other studies have used these registries to investigate similar endpoints in a similar population. E.g. a large population-based cohort study demonstrated that the IRs of VTE, DVT, and PE in 17,341 patients with AD were comparable with those in the general population.

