## 8.9. Limitations of the Research Methods

This study is based on data from Denmark, which introduces certain limitations regarding the generalizability of the findings. The Danish population is relatively homogenous in terms of ethnicity and socioeconomic structure, which may limit the direct applicability of results to more diverse populations. Additionally, Denmark has a high standard of living and a universally tax-funded healthcare system that ensures equal access to medical care. While this provides a robust setting for epidemiological research, it may not reflect healthcare access, quality, or utilization patterns in countries with different healthcare models. These contextual differences should be considered when interpreting the results and comparing them to findings from other regions or healthcare systems.

Diagnosis, comorbidities, medical history and outcomes will be identified using the ICD-8 and -10 diagnosis codes, which might be subject to potential miscoding. However, this is partly mitigated by using dermatologist verified AD diagnosis. Based on clinical experience, outcomes of this severity are unlikely to be over- or underreported. However, the events can be misdiagnosed and improperly entered in to the registries.

Typically, prescription of a medication does not necessarily indicate that the medication was taken as prescribed. Similarly over-the-counter medications will not be captured in the databases, and the effect of these cannot be elucidated.

The investigated medications are used for multiple indications, therefore it is possible that the medications, e.g. prednisolone, was prescribed for another diagnosis than AD. However, this is attempted to be counterbalanced, as patients with concurrent diagnoses where the investigated treatments also were used, were excluded from the study.

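### Table III labels the thromboembolism drug criterion as anticoagulation but codes all of ATC B01A, so a prescribed antiplatelet can confirm a DVT or PE code

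*Protocol*

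**What the plan says.** The protocol's Table III (Section 8.3) puts AT, DVT and PE in one row, with the role "AE, sec. outcomes". The DVT list ends with "I80.8, I80.9, I82.2, I82.3, I82.9". The PE and AT codes follow in the same cell, which closes with the drug criterion: "And anticoagulation therapy: ATC B01A". No ATC subgroup is listed or excluded, and arterial and venous events share the one drug criterion. The row's data source is the National Patient Registry only.

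Three other places bear on the rule:

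- Section 8.4 says that the prescription register "contains information on all filled prescriptions at community pharmacies from 1995 onwards, using the Anatomical Therapeutic Chemical (ATC) classification system". It is the source that could supply a B01A fill.
- Section 8.4 also states: "No formal validation studies of all study endpoints have been performed". The protocol gives no predictive value for these codes, with or without the drug criterion.
- Section 8.9 notes that "over-the-counter medications will not be captured in the databases".

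No other section narrows B01A or separates the venous from the arterial rule.

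**The concern.** A drug criterion is added to a thromboembolism code to remove codes that do not reflect a treated event. For DVT and PE the informative treatment is an anticoagulant, and the label says so. The code beside it also admits platelet inhibitors, which are prescribed for other reasons and do not indicate a treated venous clot. A programmer who follows the label and one who follows the code would count different events.

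The filter has most to do for I80.8 and I80.9 (phlebitis of other or unspecified site), which are weak evidence of DVT on their own. A patient with such a code and a prescribed antiplatelet meets the definition as coded.

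Venous thromboembolism is a named secondary outcome. It is reported per drug per 10,000 person-years and compared with two matched groups by Cox regression. Follow-up stops at the event of interest (Section 8.7), so a falsely confirmed code adds an event and also removes later person-time and any later true event.

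**Working it through.** **Step 1: label against code.** The label is anticoagulation therapy and the code is B01A. The content of B01A is a fact of the ATC system; the protocol does not spell it out.

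| ATC subgroup | Content | Fits the label? |
|---|---|---|
| B01AA, B01AB, B01AE, B01AF, B01AX05 | anticoagulants | yes |
| B01AC | platelet inhibitors, including low-dose aspirin | no |

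B01A includes everything in the first row, so using it in place of those subgroups can only add events, never remove them. The added DVT or PE events are those with no recorded anticoagulant fill.

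**Step 2: size.** The protocol has no figure to reproduce. All inputs below are assumptions.

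- p: PPV of the bare code; 0.60, 0.75 or 0.90.
- s: share of true venous codes with a qualifying fill; 0.90, held the same under the broad and narrow rules.
- a: share of false codes that pass through a prescribed antiplatelet; 0.10 to 0.30, set equal to antiplatelet use among patients.

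False share of counted events = (1 − p)a / [ps + (1 − p)a].

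| p | a = 0.10 | a = 0.20 | a = 0.30 |
|---|---|---|---|
| 0.60 | 0.04/0.58 = 6.9% | 0.08/0.62 = 12.9% | 0.12/0.66 = 18.2% |
| 0.75 | 0.025/0.70 = 3.6% | 0.05/0.725 = 6.9% | 0.075/0.75 = 10.0% |
| 0.90 | 0.01/0.82 = 1.2% | 0.02/0.83 = 2.4% | 0.03/0.84 = 3.6% |

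**Step 3: allow the narrow rule to be imperfect.** Step 2 assumes that no false code carries an anticoagulant fill. Now let f = 0.05 of false codes carry one, with a as the further share that passes only through an antiplatelet.

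PPV after the filter = ps / [ps + (1 − p)(f + a)].

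Inflation of counted events = [ps + (1 − p)(f + a)] / [ps + (1 − p)f].

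| p | PPV, anticoagulants only (a = 0) | PPV, whole B01A (a = 0.05 to 0.30) | Extra counted events |
|---|---|---|---|
| 0.60 | 0.964 | 0.931 to 0.794 | 3.6% to 21.4% |
| 0.75 | 0.982 | 0.964 to 0.885 | 1.8% to 10.9% |
| 0.90 | 0.994 | 0.988 to 0.959 | 0.6% to 3.7% |

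For example, at p = 0.60 and a = 0.30: 0.54/(0.54 + 0.40 × 0.35) = 0.54/0.68 = 0.794, and 0.68/0.56 = 1.214.

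**Step 4: does the filter still help?** PPV after the filter exceeds p whenever f + a is below s. The largest value used is 0.05 + 0.30 = 0.35, well below 0.90. The rule as coded therefore still improves on the bare code in every scenario, but less than an anticoagulant-only rule.

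**The case against.** Several counter-arguments carry weight.

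- **The broad code may be deliberate.** The cell also covers AT, where antiplatelets may belong, and the row cites two Danish venous thromboembolism cohort studies that cannot be checked here. Line breaks in the cell are lost, so it is an assumption, though the natural reading, that the drug text applies to all three outcomes. This argues for separate venous and arterial rules. It does not reconcile an anticoagulation label with a code that includes platelet inhibitors.
- **Timing is a SAP matter.** The row states no interval between diagnosis and fill. A reader might infer that any fill at any time counts, such as aspirin started years earlier. The protocol does not say that; it is silent, and a SAP could supply the interval. Silence on timing is not a finding by itself.
- **The filter is not defeated.** A reader might infer that it works only in patients without cardiovascular disease, or that almost any code passes in those with risk factors. That would need antiplatelet use near 100% in that group, and nothing in the protocol supports it. Aspirin bought over the counter is not captured and cannot trigger the rule.
- **Bias between groups is not shown.** A reader might infer that the hazard ratios partly measure aspirin use. The protocol gives no antiplatelet use by drug or group, and the propensity score may include age, sex and the presence of at least one cardiovascular risk factor (Section 8.7, Matching). That should reduce differences in antiplatelet use. A yes/no risk factor need not remove them, so the bias remains possible but undemonstrated.
- **The magnitudes are assumed.** This is correct: no input in the working comes from the documents.
- **The outcome is secondary** and the study is called descriptive. That limits the weight of the point but does not remove the error.

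**Conclusion.** The concern holds as a mismatch between label and code in a stated outcome definition. As written, Table III allows a prescribed antiplatelet to confirm a DVT or PE code without any anticoagulant treatment, with most consequence for I80.8 and I80.9.

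The broader code can only add events, and those it adds lack a recorded anticoagulant fill, so extra false positives are expected. Under the assumptions in the working, about 1–4% of counted venous events are false at a bare-code PPV of 90%, 4–10% at 75% and 7–18% at 60%. The true size is unknown. MACE and malignancy do not use this criterion and are unaffected. The correction is worth making before data extraction, since it concerns a named safety outcome and costs little.

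**What to change.** Split the Table III cell.

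- **DVT and PE:** replace B01A by the anticoagulant subgroups B01AA, B01AB, B01AE, B01AF and B01AX05, and require the fill in a stated period after the diagnosis date. The length of that period can be set in the SAP.
- **AT:** give it its own drug criterion, in which antiplatelets may remain.
- **Data source:** add the Register of Medicinal Product Statistics to the row.

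Do not require the absence of earlier anticoagulant fills in the main definition. That would drop true events in patients already anticoagulated, including recurrences on treatment. It could serve at most as a sensitivity analysis.

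The cost is one table cell and a narrower ATC filter, with no new data. The downside is some lost sensitivity. True venous events with no community-pharmacy anticoagulant fill after the diagnosis, such as deaths before any fill, are not counted. A few of these would have been counted by chance through an antiplatelet fill under the present code.
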